
Objectives	Endpoints

 To explore changes in the severity of liver disease. 	
 Changes in fibrosis (according to Fibroscan liver stiffness measurements) at EOSI and the end of the FU period versus baseline.

 To explore efficacy of the study intervention in terms of changes in HBV RNA and hepatitis B core-related antigen (HBcrAg) levels during the study intervention and FU period. 	
 Changes from baseline in HBV RNA and HBcrAg levels over time.

 To explore the relationship of PK with selected pharmacodynamic (PD) parameters of efficacy and safety. 	
 Relationship of various PK parameters with selected efficacy and safety endpoints.

 To explore the effect of PegIFN-α2a coadministration on the PK of JNJ-3989 (JNJ-3924 and JNJ-3976) and JNJ-6379^e, as applicable (PK substudy). 	
 Effect of PegIFN-α2a coadministration on the PK of JNJ-3989 (JNJ-3924 and JNJ-3976) and JNJ-6379, as applicable.

 To explore the HBV genome sequence during the study intervention and FU period. 	
 Assessment of intervention-associated mutations over time.

 To explore HBV-specific T-cell responses during the study intervention and FU period.^c 	
 Changes from baseline in HBV-specific peripheral blood T-cell responses over time.^c

 To explore the efficacy of NA re-treatment in participants who meet the criteria for NA re-treatment. 	
 Proportion of participants who reach HBV DNA <LLOQ after re-start of NA treatment during the FU period.

^a In HBeAg-positive participants only.

^b For the definition of virologic breakthrough, refer to Section 10.1, Appendix 1: Abbreviations and Definitions of Terms.

^c Peripheral blood mononuclear cell (PBMC) samples for immune analyses will be collected at selected sites only.

^d As of Protocol Amendment 3, JNJ-6379 has been removed as study intervention and the study will continue with JNJ-3989, NA and PegIFN- α 2a only. Participants had to stop JNJ-6379 treatment immediately.

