^e Not all participants completed treatment with JNJ-6379, as JNJ-6379 has been removed as study intervention with the implementation of Protocol Amendment 3.

Hypothesis

As this is an exploratory single-arm study, no formal statistical hypothesis has been formulated.

OVERALL DESIGN

This ISA describes a Phase 2a study of the combination regimen of JNJ-3989, NA, and PegIFN- α 2a. Prior to Protocol Amendment 3, the study intervention also included JNJ-6379. It is a companion document to the Master Protocol PLATFORMPAHPB2001, which describes the common design elements of the Platform study in participants with chronic hepatitis B (CHB). This ISA describes specific and/or additional protocol elements applicable to this open-label, single-arm, multicenter, interventional study to evaluate the efficacy, safety, tolerability, and PK of the combination of JNJ-3989, NAs, and PegIFN- α 2a in approximately 50 patients with CHB.

Note that as of Protocol Amendment 3, JNJ-6379 has been removed as study intervention and the study will continue with JNJ-3989, NA and PegIFN- α 2a only. Participants had to stop JNJ-6379 treatment immediately.

This open-label study will be conducted in 4 periods:

- Screening Period (4 weeks [if necessary, can be extended to a maximum of 8 weeks decided on a case-by-case basis and in agreement with the sponsor]).
- Treatment Period 1 (12 weeks) consisting of combination treatment with JNJ-3989 + NA.
- Treatment Period 2 (12 weeks) adding PegIFN- α 2a to the combination treatment regimen of Treatment Period 1.
- Follow-up (FU) Period (48 weeks).

The total duration of individual participation will be up to 76 weeks (including 4 weeks of screening).

Enrolled participants will start Treatment Period 1 with the following combination treatment regimen for a duration of 12 weeks:

200 mg JNJ-3989 (subcutaneous injection every 4 weeks [Q4W]) +

NA (tablets QD): tenofovir disoproxil (245 mg), or tenofovir alafenamide (TAF; 25 mg), or entecavir (ETV; 0.5 mg).

At Week 12, participants who still meet the eligibility criteria for PegIFN- α 2a (see Section 5.2, Exclusion Criteria) will start Treatment Period 2 for a duration of 12 weeks:

200 mg JNJ-3989 (subcutaneous injection Q4W) +

NA (tablets QD): tenofovir disoproxil (245 mg), or TAF (25 mg), or ETV (0.5 mg) +

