180 μ g PegIFN- α 2a (subcutaneous injection once weekly). Participants no longer meeting the PegIFN- α 2a eligibility criteria at Week 12 will continue with the Period 1 treatment until Week 24.

At Week 24, all participants will stop treatment with JNJ-3989 + PegIFN- α 2a and start the FU Period. If the protocol-defined NA treatment completion criteria (HBsAg <10 IU/mL, and HBeAg-negative, and HBV DNA <LLOQ, and ALT <3x upper limit of normal [ULN]) have been met at Week 24, NA will be stopped at the next scheduled visit (ie, FU Week 2), otherwise NA treatment will continue during the complete FU Period. Participants who meet the protocol-defined NA treatment completion criteria will be monitored closely during the 48-week FU Period and should re-start NA treatment immediately if NA re-treatment criteria are met, as specified below.

The investigator should consider to re-start NA treatment per local standard of care at the EOS visit (Follow-up Week 48) for participants who met the NA treatment completion criteria at Week 24, who did not re-start NA treatment during the follow-up phase, and who did not achieve and maintain HBsAg seroclearance. NA will not be provided by the sponsor after the final study visit.

All participants will have sparse PK sampling during the treatment periods. Participants who consent to participate in the intensive PK substudy (optional) will also undergo intensive PK sampling.

Participants will be considered to have completed the study if they have completed all the assessments of the end of study (EOS) visit (ie, FU Week 48).

An internal data review committee (DRC) will be commissioned for monitoring safety of participants enrolled in this study. In addition, an Independent Flare Expert Panel (IFLEP) will be appointed.

NA Re-treatment Criteria and Monitoring After Stopping of NA

Participants who meet the protocol-defined NA treatment completion criteria will be monitored closely during the FU Period.

After stopping NA treatment, participants should be monitored as follows:

- Regular monitoring visits will be every 4 weeks during the follow-up phase in accordance with the Schedule of Activities.
- A post-treatment HBV DNA value of >20,000 IU/mL should trigger re-testing of ALT/AST, HBV DNA, and total and direct bilirubin within a maximum of 7 days from receipt of the data and further repeats as necessary (ie, weekly until HBV DNA returns to <20,000 IU/mL).

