 - qq. *Visits at follow-up Week 16, 20, 28, 32, 40, and 44 are optional for participants who continue NA treatment and for participants who have restarted NA treatment during the follow-up period, provided that their HBV DNA and ALT values are stable.*
 - rr. Liver function tests only.
 - ss. Urine pregnancy tests will be provided to the participants for at home use as necessary to ensure urine pregnancy tests are performed at least every 4 weeks. Participants will report the results to the study site personnel at the next visit, and these will be added to the source documents. If positive, the participant should contact the site immediately.
 - tt. No JNJ-3989/PegIFN- α 2a will be administered or dispensed during follow-up. Administration/Dispensation of NA is only applicable for participants who could not stop NA treatment, or for those who met the NA re-treatment criteria. In between study visits, participants will take NA at home and they will bring their NA treatment with them to each study visit.
 - uu. If the NA treatment completion criteria are met at Week 24, treatment with NA will be stopped at FU Week 2.
 - vv. Available historical data on HBeAg status before start of NA treatment will be collected in the CRF.
 - ww. A urinalysis and urine chemistry sample will be taken at FU Week 2. In case of abnormalities, the tests should be repeated at the following visits.
 - xx. Includes close monitoring for neuropsychiatric adverse events during the PegIFN- α 2a treatment period. Participants who develop a neuropsychiatric adverse event during PegIFN- α 2a treatment, will be monitored closely until the neuropsychiatric adverse event resolves, with frequent (at least weekly) follow-up phone calls.
 - yy. NA treatment should be re-started in accordance with the NA re-treatment criteria (see Section 6.7.1, NA Re-treatment Criteria and Monitoring After Stopping of NA and Section 10.12 Appendix 12, for guidance after stopping NA treatment).
 - zz. Participants enrolled before Protocol Amendment 3 was in effect, may have received JNJ-6379 as part of their study intervention.

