6.7.1. NA Re-treatment Criteria and Monitoring After Stopping of NA

Participants who meet the protocol-defined NA treatment completion criteria outlined in Section 6.6, Study Intervention Completion at Week 24, will be monitored closely during the FU Period.

After stopping NA treatment, participants should be monitored as follows:

- Regular monitoring visits will be every 4 weeks during the follow-up phase in accordance with the [Schedule of Activities](#).
- A post-treatment HBV DNA value of >20,000 IU/mL should trigger re-testing of ALT/AST, HBV DNA, and total and direct bilirubin within a maximum of 7 days from receipt of the data and further repeats as necessary (ie, weekly until HBV DNA returns to <20,000 IU/mL).
- A post-treatment HBV DNA value of >2,000 IU/mL (but <20,000 IU/mL) should trigger a re-test within 14 days from receipt of the data and further repeats as necessary (ie, every other week until HBV DNA returns to <2,000 IU/mL).
- A post-treatment ALT value of >5x ULN should trigger re-testing of ALT, AST, ALP, total and direct bilirubin, INR, albumin, and HBV DNA on a weekly basis until ALT and AST levels have returned to <5x ULN.

After stopping NA treatment, participants should re-start NA treatment:

- Immediately with signs of decreasing liver function based on laboratory findings (eg, INR, direct bilirubin) or clinical assessment (eg, ascites, hepatic encephalopathy).
- Immediately with an HBV DNA value of >100,000 IU/mL (irrespective of confirmation and/or ALT increase).
- With confirmed post-treatment HBeAg seroreversion (HBeAg positive after it was negative at NA completion).
- With confirmed* post-treatment increases in HBV DNA >2,000 IU/mL and ALT >5x ULN.

- With confirmed* post-treatment increases in HBV DNA >20,000 IU/mL.

* *At least 4 weeks apart – frequency of visits as described above*

Note: Additional re-testing and/or earlier restarting of NA treatment is at the investigator's discretion, even if the above cut-offs are not yet met.

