5.4.2.1.10. Suppressed HBV DNA

The count and proportion of participants (and associated 90% CI) with HBV DNA <LLOQ (overall and separately for HBV DNA detectable and HBV DNA TND) will be evaluated by analysis phase over time.

The count and proportion of participants (and associated 90% CI) with HBV DNA <LLOQ (overall and separately for HBV DNA detectable and HBV DNA TND) will be evaluated at each of the FU Weeks 12, 24, 36, and 48, respectively, after stopping all study interventions at the end of treatment period 2 and without restarting NA treatment.

The count and proportion of participants (and associated 90% CI) with HBV DNA <LLOQ (overall and separately for HBV DNA detectable and HBV DNA TND) will be evaluated at each of the following off-treatment timepoints: 12, 24, 36, and 48 weeks, respectively, after stopping all study interventions and without restarting NA treatment. In an additional summary, these proportions will be calculated with the denominator including only those participants who have reached the off-treatment timepoint (week 12, 24, 36 or 48), and have stopped all interventions including NA and have not restarted NA prior to the timepoint of interest.

The count and proportion of participants (and associated 90% CI) with HBV DNA <LLOQ (overall and separately for HBV DNA detectable and HBV DNA TND) after restart of NA treatment during follow-up will also be presented.

The number of occurrences each subject has HBV DNA <LLOQ (overall and separately for HBV DNA detectable and HBV DNA TND) will be determined and summarized using frequency distributions and descriptive statistics. Additionally, the number of occurrences will be displayed graphically. For all time points, HBV DNA <LLOQ will be analyzed using the observed case data. LOCF will be used for selected time points (Section 5.4.2.1.1), if there is at least 10% of the participants with missing HBV DNA results for the selected time points.

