5.4.2.3. Time to Event Endpoints

The Kaplan-Meier method will be used to estimate and plot the cumulative incidence and estimate the median time with 90% CI. In addition, the number and percentage of participants who had an event or were censored will be reported.

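### HBV DNA re-suppression after NA re-start is a plain proportion with no fixed time since re-start, so it depends partly on when participants re-started

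*Protocol*

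**What the plan says.** The objective (Protocol 1.1 and 3; SAP 1.1) is to explore how well NA re-treatment works in participants who meet the re-treatment criteria. The endpoint is "Proportion of participants who reach HBV DNA <LLOQ after re-start of NA treatment during the FU period". In SAP 5.4.2.1.10 the matching analysis is a count and proportion, overall and split by target detected or not detected, which "after restart of NA treatment during follow-up will also be presented". No time since re-start, minimum follow-up, denominator or censoring rule is attached to it.

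The timing comes from elsewhere in the protocol. The rule for participants who satisfy the completion criteria when treatment ends is: "NA will be stopped at the next scheduled visit (ie, FU Week 2), otherwise NA treatment will continue during the complete FU Period" (Protocol 1.1). After the stop, "Regular monitoring visits will be every 4 weeks during the follow-up phase" (Protocol 6.7.1). Re-start can follow at any point in the 48-week follow-up. Some triggers act at once; the two confirmed HBV DNA triggers need values at least 4 weeks apart. Once NA is re-started, follow-up runs to the end of study or to clinical stabilization, whichever is later.

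The Schedule of Activities (footnote qq) adds that "Visits at follow-up Week 16, 20, 28, 32, 40, and 44 are optional" for re-started participants, provided HBV DNA and ALT are stable.

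**The concern.** The proportion is meant to show whether NA regains control after relapse. Without a clock that starts at re-start, it also measures how much follow-up was left when the relapse happened. Two cohorts with the same response to NA would report different figures if one relapsed early and the other late.

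The figure can also drift between analyses. SAP Table 10 provides exploratory endpoints from the first interim analysis onward, so the proportion may change between cut-offs simply because follow-up after re-start has lengthened. With few re-starts, one or two late ones can visibly move a raw percentage.

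**Working it through.** The plan gives no figure for time on re-started NA, so there is none to reproduce.

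**1. Time left after re-start.** Formula: (337 − FU target day of the re-start visit) / 7, with target days from the Schedule of Activities and SAP Table 4.

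- FU Week 4: (337 − 29)/7 = 44 weeks, 11 later scheduled HBV DNA visits
- FU Week 8: (337 − 57)/7 = 40 weeks, 10 later visits
- FU Week 24: (337 − 169)/7 = 24 weeks, 6 later visits
- FU Week 36: (337 − 253)/7 = 12 weeks, 3 later visits
- FU Week 44: (337 − 309)/7 = 4 weeks, 1 later visit

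An unscheduled re-start just after the FU Week 2 stop would have (337 − 15)/7 = 46 weeks.

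**2. Distance to fall.** The HBV DNA LLOQ is 20 IU/mL (SAP Table 5). From the thresholds in Protocol 6.7.1:

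- 2,000 IU/mL (with ALT >5x ULN): log10(2,000/20) = 2.0
- 20,000 IU/mL: log10(20,000/20) = 3.0
- 100,000 IU/mL: log10(100,000/20) = 3.7

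**3. Pace of decline.** Protocol 2.2.3.1 offers two reference groups, both untreated at screening.

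- HBeAg-negative, mean baseline 4.89 to 5.40 log10 IU/mL: many were below LLOQ from Week 4. The text does not split this by arm.
- HBeAg-positive on placebo + NA: mean decline 5.21 log10 at Week 24, or 5.21/24 = 0.217 per week if linear. Falls of 3.0 and 3.7 log10 then take 13.8 and about 17 weeks.

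The first group is closer, because the completion criteria require participants to be HBeAg-negative when NA stops (Protocol 6.6).

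**4. Share with too little time.** Assumptions: re-starts spread evenly over FU Weeks 8-48 (40 weeks), every participant eventually re-suppressed, observation ending at FU Week 48. If t weeks are needed, the share is t/40.

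- t = 4: 4/40 = 10%, so a true 100% would show as about 90%
- t = 17: 17/40 = 43%, so a true 100% would show as about 57%
- All re-starts at FU Week 8 and t no more than 17: 0%, since 40 weeks remain

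**5. Varying re-start timing.** Assumption: exponential time to <LLOQ with median m weeks, λ = ln 2/m. With re-starts uniform over the last T weeks, the crude proportion by FU Week 48 is 1 − (1 − e^(−λT))/(λT). With a common remaining time t it is 1 − e^(−λt).

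| Re-start timing | m = 4 | m = 8 | m = 12 | m = 24 |
|---|---|---|---|---|
| All at FU Week 8 (t = 40) | 99.9% | 97% | 90% | 69% |
| Uniform, FU Weeks 4-48 (T = 44) | 87% | 74% | 64% | 43% |
| Uniform, FU Weeks 36-48 (T = 12) | 58% | 38% | 28% | 16% |
| Fixed 24 weeks after re-start, any timing | 98% | 88% | 75% | 50% |

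Within a column NA works equally well; the first three rows differ only in re-start timing. The last row does not depend on it.

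**6. Whether another planned analysis covers this.** SAP 5.4.1.3.5 measures time to HBV DNA <LLOQ from first study intervention intake, and its second version censors at NA re-treatment. Anyone who stopped NA under the Week 24 criteria already had HBV DNA <LLOQ then, so the event precedes any re-start. The LOCF rules in SAP 5.4.2.1.1 are tied to FU Weeks 12, 24, 36 and 48, not to time since re-start.

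**The case against.** The strongest reply is that a reader could easily infer more than the documents support. Four such readings should be set aside.

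- **Late re-starts are scored as NA failures.** Nothing says so. The SAP analyses exploratory endpoints on observed cases without imputation (5.5, 5.5.2), and secondary endpoints on observed cases by default (5.4). A re-start with no later value has no observed outcome. What stands is narrower: a value that is present and still at or above LLOQ is not missing, so the observed-case rule does not remove it.
- **Observation stops at FU Week 48.** Protocol 6.7.1 can extend follow-up to clinical stabilization, and the last window in SAP Table 4 is open-ended. This eases the truncation but does not end it, because stabilization is not defined as HBV DNA <LLOQ. Re-start considered at the end-of-study visit is described separately from re-start during follow-up, so the lower end of the range is better called near zero than zero.
- **The shortfall is 43%.** That end uses a linear rate from HBeAg-positive, untreated participants with mean baselines of 7.65 to 8.24 log10. Re-start from 2,000 IU/mL, or earlier at the investigator's discretion, leaves less to fall. No source supports an even spread of re-starts.
- **This is the only evidence on rescue.** ALT normalization after NA re-treatment is also summarized (SAP 5.4.2.1.12), and HBV DNA spaghetti plots show individual courses.

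The optional visits add little to the bias in the proportion. They apply only when values are stable, and FU Week 48 remains scheduled. They matter more for the precision of event dates.

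Finally, the endpoint is exploratory in a single-arm study with no hypothesis, and re-starts are likely to be few. That limits the severity, not the validity of the point.

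**Conclusion.** The point holds in limited form. The proportion has no fixed time since re-start, no stated denominator and no censoring rule, while time from re-start to FU Week 48 varies from about 44 weeks to near zero. The result mixes response to NA with timing of re-start, and no other planned analysis separates them.

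The direction is downward for late re-starts last seen at or above LLOQ. The size cannot be fixed from the documents. About 10% of re-starts with too little time is the more relevant illustration; it assumes evenly spread re-starts over FU Weeks 8-48, eventual re-suppression of all, 4 weeks needed and no values after FU Week 48. Slower re-suppression gives more, and early re-starts give almost none. Severity is low.

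**What to change.** In SAP 5.4.1.3 and 5.4.2.1.10, define the denominator as participants who re-started NA during follow-up. Add time from the re-start date to first HBV DNA <LLOQ, censored at the last HBV DNA value and including any collected after FU Week 48 under Protocol 6.7.1. Use the method already in SAP 5.4.2.3: "The Kaplan-Meier method will be used to estimate and plot the cumulative incidence". Report the estimate with 90% CI and number at risk at 4, 12 and 24 weeks after re-start, and keep the raw count beside weeks of follow-up since re-start.

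This follows the SAP's own practice. The off-treatment HBV DNA summaries in 5.4.2.1.10 already include a denominator limited to participants who reached the time point, and 5.4.1.3.7 already starts a clock at the last intake for off-treatment flares.

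The cost is SAP wording and one table from data already collected. The downsides are wide intervals from few re-starts, and event times known only to the visit interval, which can reach 12 weeks where optional visits are skipped.

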1.2. Schema

[figure not shown]
Figure 1: Schematic Overview of the Study – Prior to Protocol Amendment 3

ALT: alanine aminotransferase ; DNA: deoxyribonucleic acid; EOS: end of study; EOSI: end of study intervention; FU: follow-up; HBeAg: hepatitis B e antigen; HBsAg: hepatitis B surface antigen; HBV: hepatitis B virus; JNJ-3989: JNJ-73763989; JNJ-6379: JNJ-56136379; LLOQ: lower limit of quantification; n: number of participants; NA: nucleos(t)ide analog; PegIFN- α 2a: pegylated interferon alpha-2a; ULN: upper limit of normal; Q4W: every 4 weeks; QD: once daily; QW: once weekly.

^a If NA treatment completion criteria (HBsAg <10 IU/mL, and HBeAg-negative, and HBV DNA <LLOQ, and ALT <3x ULN) have been met at Week 24, NA will be stopped at the next scheduled visit (ie, FU Week 2), otherwise NA treatment will continue during the complete FU period.

Figure 2: Schematic Overview of the Study – As of Protocol Amendment 3

ALT: alanine aminotransferase ; DNA: deoxyribonucleic acid; EOS: end of study; EOSI: end of study intervention; FU: follow-up; HBeAg: hepatitis B e antigen; HBsAg: hepatitis B surface antigen; HBV: hepatitis B virus; JNJ-3989: JNJ-73763989; LLOQ: lower limit of quantification; n: number of participants; NA: nucleos(t)ide analog; PegIFN-α2a: pegylated interferon alpha-2a; ULN: upper limit of normal; Q4W: every 4 weeks; QD: once daily; QW: once weekly.

^a If NA treatment completion criteria (HBsAg <10 IU/mL, and HBeAg-negative, and HBV DNA <LLOQ, and ALT <3x ULN) have been met at Week 24, NA will be stopped at the next scheduled visit (ie, FU Week 2), otherwise NA treatment will continue during the complete FU period.

1.3. Schedule of Activities

Below is a comprehensive schedule of activities that will be performed in this study, including that from the Master Protocol PLATFORMPAHPB2001. All differences with the Master Protocol PLATFORMPAHPB2001 (including the ISA-specific activities) are highlighted (colored fill). Guidance in the event of disruption to the study conduct is provided in Section 10.10, Appendix 10: Study Conduct During a Natural Disaster.

Study Period	Screening	Treatment Period 1 ^{a,d,e}				Treatment Period 2 ^{a,d,e}					Follow-up ^{a,e,gg}														
		D1 ^c	W2	W4	W8	W12	W14	W16	W20	W24 /EOSI /WD ^e	FU W2	FU W4	FU W8	FU W12	FU W16 ^{gg}	FU W20 ^{gg}	FU W24	FU W28 ^{gg}	FU W32 ^{gg}	FU W36	FU W40 ^{gg}	FU W44 ^{gg}	FU W48 /EOS /WD ^{e,aaa}		
Visit Day (D)/Week (W)	W-4 to 0 ^b																								
Study Day (Window)	-28 to 0	1	15 +/-2d	29 +/-2d	57 +/-2d	85 +/-2d	99 +/-3d	113 +/-3d	141 +/-3d	169 +/-3d	15 +/-4d	29 +/-4d	57 +/-4d	85 +/-4d	113 +/-4d	141 +/-4d	169 +/-4d	197 +/-4d	225 +/-4d	253 +/-4d	281 +/-4d	309 +/-4d	337 +/-4d		
Screening/Administrative																									
ICF (including ICF for optional PK) ^f	X																								
ICF for optional pharmacogenomic samples	X																								
Inclusion/exclusion criteria ^g	X																								
PegIFN-α2a eligibility	X					X ^{pp}																			
Prestudy therapy (including prior anti-HBV therapy)	X																								
Medical/surgical history and demographics ^h	X																								
Preplanned surgery/procedure(s)	X																								
Fibroscan or liver biopsy ⁱ	X																								
Ultrasound ^l	X																								
Serum IgM anti-HBc antibody test	X																								
HBV genotype ^k		X																							
Study Intervention																									
Administration of JNJ-3989		X		X	X	X		X	X																
Intake of JNJ-6379 ^{m,tt,zz}		X	X	X	X	X	X	X	X	X ^l															
Intake of NA ^{m,tt}		X	X	X	X	X	X	X	X	X ^l	(X)	(X)	(X)	(X)	(X)	(X)	(X)	(X)	(X)	(X)	(X)	(X)	(X)	(X)	(X) ^l
Dispensation of JNJ-6379 ^{tt,zz}		X		X ^{xx}	X ^{xx}	X ^{xx}		X ^{xx}	X ^{xx}																
Dispensation of NA ^{tt}		X		X	X	X		X	X	X ^l		(X)	(X)	(X)	(X)	(X)	(X)	(X)	(X)	(X)	(X)	(X)	(X)	(X)	

Study Period	Screening	Treatment Period 1 ^{a,d,e}				Treatment Period 2 ^{a,d,e}					Follow-up ^{a,e,qg}													
		W-4 to 0 ^b	D1 ^c	W2	W4	W8	W12	W14	W16	W20	W24 /EOSI /WD ^e	FU W2	FU W4	FU W8	FU W12	FU W16 ^{gg}	FU W20 ^{gg}	FU W24	FU W28 ^{gg}	FU W32 ^{gg}	FU W36	FU W40 ^{gg}	FU W44 ^{gg}	FU W48 /EOS /WD ^e _{aaa}
Visit Day (D)/Week (W)	W-4 to 0 ^b	D1 ^c	W2	W4	W8	W12	W14	W16	W20	W24 /EOSI /WD ^e	FU W2	FU W4	FU W8	FU W12	FU W16 ^{gg}	FU W20 ^{gg}	FU W24	FU W28 ^{gg}	FU W32 ^{gg}	FU W36	FU W40 ^{gg}	FU W44 ^{gg}	FU W48 /EOS /WD ^e _{aaa}	
Study Day (Window)	-28 to 0	1	15 +/-2d	29 +/-2d	57 +/-2d	85 +/-2d	99 +/-3d	113 +/-3d	141 +/-3d	169 +/-3d	15 +/-4d	29 +/-4d	57 +/-4d	85 +/-4d	113 +/-4d	141 +/-4d	169 +/-4d	197 +/-4d	225 +/-4d	253 +/-4d	281 +/-4d	309 +/-4d	337 +/-4d	
Administration of PegIFN-α2a ^{m,tt}						X	X	X	X															
Dispensation of PegIFN-α2a ^{m,tt}						X		X	X															
Provide PegIFN-α2a self-injection tracker ⁿ						X																		
Review PegIFN-α2a self-injection tracker ^o							X	X	X	X														
Study intervention accountability				X	X	X		X	X	X		(X)	(X)	(X)	(X)	(X)	(X)	(X)	(X)	(X)	(X)	(X)	(X)	(X)
Assess NA treatment completion criteria											X ^{uu}													
Continuous assessment of NA re-treatment criteria, as applicable												(X)	(X)	(X)	(X)	(X)	(X)	(X)	(X)	(X)	(X)	(X)	(X)	(X)
Safety Assessments																								
Complete physical examination ^p	X									X														
Symptom-directed physical examination, including body weight		X	X	X	X	X	X	X	X		X	X	X	X	X	X	X	X	X	X	X	X	X	X
Ophthalmic examination (including funduscopy)	X				X ^q					X ^r														
Vital signs ^s	X	X	X	X	X	X	X	X	X	X	X	X	X	X	X	X	X	X	X	X	X	X	X	X
Triplicate 12-lead ECG ^t	X	X		X		X				X		X												
Injection site reactions (for JNJ-3989 and/or PegIFN-α2a)		X	X	X	X	X	X	X	X	X														
Liver ultrasound ^u		(X)								X							X							X
Clinical Laboratory Tests																								
Hematology ^w	X	X	X	X	X	X	X	X	X	X	X	X	X	X	X		X	X		X		X	X	X
Blood chemistry (including liver function tests) ^{v,x,y}	X	X	X	X	X	X	X	X	X	X	X	X	X	X ^{rr}	X ^{rr}	X ^{rr}	X	X ^{rr}	X ^{rr}	X	X	X	X	X
Blood coagulation	X	X		X	X	X	X	X	X	X	X	X		X			X			X		X	X	X
Urinalysis ^z	X	X		X	X	X	X	X	X	X	X ^{ww}	(X)	(X)	(X)	(X)	(X)	(X)	(X)	(X)	(X)	(X)	(X)	(X)	X
Urine chemistry ^{aa}	X	X		X	X	X	X	X	X	X	X ^{ww}	(X)	(X)	(X)	(X)	(X)	(X)	(X)	(X)	(X)	(X)	(X)	(X)	X

Study Period	Screenin g	Treatment Period 1 ^{a,d,e}				Treatment Period 2 ^{a,d,e}					Follow-up ^{a,e,qg}													
		D1 ^c	W2	W4	W8	W12	W14	W16	W20	W24 /EOSI /WD ^e	FU W2	FU W4	FU W8	FU W12	FU W16 ^{qg}	FU W20 ^{qg}	FU W24	FU W28 ^{qg}	FU W32 ^{qg}	FU W36	FU W40 ^{qg}	FU W44 ^{qg}	FU W48 /EOS /WD ^e aaa	
Visit Day (D)/Week (W)	W-4 to 0 ^b	1	15 +/-2d	29 +/-2d	57 +/-2d	85 +/-2d	99 +/-3d	113 +/-3d	141 +/-3d	169 +/-3d	15 +/-4d	29 +/-4d	57 +/-4d	85 +/-4d	113 +/-4d	141 +/-4d	169 +/-4d	197 +/-4d	225 +/-4d	253 +/-4d	281 +/-4d	309 +/-4d	337 +/-4d	
Renal biomarkers ^{bb}		X				X				X														
Testing for hepatitis A, B, C, D, and E virus, HIV-1 and -2 ^y	X																							
FSH test (postmenopausal women only) ^{dd}	X																							
AFP test ^{y,cc}	X									X							X							X
Hemoglobin A1c test	X																							
Serum pregnancy test (women of childbearing potential only)	X																							
Urine pregnancy test (women of childbearing potential)		X		X	X	X	X	X	X	X		X	X	X ^{ss}	X ^{ss}	X	X ^{ss}	X ^{ss}	X ^{ss}	X ^{ss}	X ^{ss}	X ^{ss}	X ^{ss}	X
TSH and T4	X				X																			
Efficacy Evaluations																								
Fibroscan ^{ee}		(X)								(X)							(X)							(X)
HBV Virology																								
Blood sampling for HBV DNA ^{yy}	X	X		X	X	X	X	X	X	X	X	X	X	X	X	X	X	X	X	X	X	X	X	X
Blood sampling for HBV RNA ^{ff}	X	X		X	X	X	X	X	X	X	X	X		X			X							X
Sampling for viral genome sequencing ^{gg}	X	X				X				X				X		X		X	X		X			X
HBV Serology																								
Blood sampling for:																								
Anti-HBs and anti-HBe	X	X			X					X		X		X			X			X				X
HBsAg and HBeAg (qualitative)	X	X			X					X				X			X							X
HBsAg (quantitative)	X	X		X	X	X	X	X	X	X	X	X	X	X	X	X	X	X	X	X	X	X	X	X
HBeAg (quantitative) ^{vv}	X	X		X	X	X	X	X	X	X	X	X	X	X	X	X	X	X	X	X	X	X	X	X
HBcrAg ^{ff}	X	X		X	X	X		X	X	X		X		X			X			X				X
Exploratory serology ^{hh}	X	X		X	X	X	X	X	X	X	X	X	X	X	X	X	X	X	X	X	X	X	X	X

Study Period	Screenin g	Treatment Period 1 ^{a,d,e}				Treatment Period 2 ^{a,d,e}					Follow-up ^{a,e,gg}														
		D1 ^c	W2	W4	W8	W12	W14	W16	W20	W24 /EOSI /WD ^e	FU W2	FU W4	FU W8	FU W12	FU W16 ^{gg}	FU W20 ^{gg}	FU W24	FU W28 ^{gg}	FU W32 ^{gg}	FU W36	FU W40 ^{gg}	FU W44 ^{gg}	FU W48 /EOS /WD ^e aaa		
Visit Day (D)/Week (W)	W-4 to 0 ^b																								
Study Day (Window)	-28 to 0	1	15 +/-2d	29 +/-2d	57 +/-2d	85 +/-2d	99 +/-3d	113 +/-3d	141 +/-3d	169 +/-3d	15 +/-4d	29 +/-4d	57 +/-4d	85 +/-4d	113 +/-4d	141 +/-4d	169 +/-4d	197 +/-4d	225 +/-4d	253 +/-4d	281 +/-4d	309 +/-4d	337 +/-4d		
Clinical Pharmacology Assessments																									
Blood sampling for sparse PK of JNJ-3989 and optionally NA and PegIFN-α2a ⁱⁱ		X ^{jj}		X ^{jj,ll}		X ^{jj}			X ^{jj,ll}																
Blood sampling for intensive PK of JNJ-3989 and optionally NA and PegIFN-α2a (PK substudy) ^{kk}				X					X																
Exploratory Host Biomarkers																									
Whole blood RNA gene expression		X				X	X	X		X														X	
Whole blood single cell profiling		X			X	X				X		X	X	X			X			X				X	
Host serum proteins (eg, cytokines)		X		X	X	X		X	X	X		X	X	X			X			X				X	
Antidrug antibodies (to JNJ-3989 and optionally PegIFN-α2a)		X			X			X		X				X			X							X	
Immune Monitoring																									
Immune cells (PBMCs) (selected sites only) ^{mm}		X				X				X		X		X			X							X	
Pharmacogenomics (DNA)																									
HLA typing		X																							
Exploratory host genotyping (optional) ⁿⁿ		X																							
Epigenetic research (optional) ⁿⁿ		X				X				X		X		X			X							X	
Ongoing Participant Review																									
Concomitant therapy ^{oo}		X	X	X	X	X	X	X	X	X	X	X	X	X	X	X	X	X	X	X	X	X	X	X	X
Adverse events ^{oo, xx}		X	X	X	X	X	X	X	X	X	X	X	X	X	X	X	X	X	X	X	X	X	X	X	X

General Note: The ECGs should be completed before any tests, procedures or other consultations for that visit.

For Japan only, twice weekly visits are to be scheduled during the first week of treatment with PegIFN-α2a (ie, Week 12), followed by weekly visits up to Week 23, for assessment of safety (injection site reactions, physical examination, ophthalmic examination [when indicated], vital signs), hematology (only up to Week 20), concomitant

therapy and adverse events. During Week 12 (first 2 visits with PegIFN- α 2a), the study day visit window is +/-2d. After Week 12, the study day visit window is +/-3d until Week 24.

AFP: alpha-fetoprotein; ALP: alkaline phosphatase; ALT: alanine aminotransferase; AST: aspartate aminotransferase; CKD-EPI: Chronic Kidney Disease Epidemiology Collaboration; CRF: case report form; CT: computed tomography; D/d: day; DAIDS: Division of Acquired Immunodeficiency Syndrome; DBP: diastolic blood pressure; DNA: deoxyribonucleic acid; ECG: electrocardiogram; eGFR: estimated glomerular filtration rate; EOS: end of study; EOSI: end of study intervention; FSH: follicle-stimulating hormone; FU: follow-up; GI = giga; HBe: hepatitis B core protein; HBe(Ag): hepatitis B e (antigen); HBcrAg: hepatitis B core-related antigen; HBs(Ag): hepatitis B surface (antigen); HBV: hepatitis B virus; HCC: hepatocellular carcinoma; HIV-1 (-2): human immunodeficiency virus type 1 (type 2); HLA: human leukocyte antigen; ICF: informed consent form; IgM: immunoglobulin M; INR: International Normalized Ratio; ISA: intervention-specific appendix; MRI: magnetic resonance imaging; NA: nucleos(t)ide analog; PBMC: peripheral blood mononuclear cells; PegIFN- α 2a: pegylated interferon alpha-2a; PK: pharmacokinetic; RBC: red blood cell; RNA: ribonucleic acid; SBP: systolic blood pressure; T4: thyroxine; TSH: thyroid stimulating hormone; ULN: upper limit of normal; W: week; WD: withdrawal.

- a. All study visits are to be scheduled relative to the baseline (Day 1) visit date. All follow-up study visits are to be scheduled relative to the Week 24/EOSI visit. An unscheduled visit can be performed upon the investigator's discretion, in case of HBV DNA elevations, ALT elevations, other signs of worsening of liver disease, or for any other reason.
- b. If necessary (eg, for operational reasons), the Screening Period may be extended up to a maximum of 8 weeks in agreement with the sponsor.
- c. Day 1 samples are to be collected before the first dose of study intervention.
- d. All assessments (with the exception of the sparse and intensive PK samples) should be performed before administration/intake of JNJ-3989 and NA. If applicable, weekly PegIFN- α 2a administration should preferably be done on the same day of the week in the evening by self-injection. If desired, participants can also choose to have the administration of PegIFN- α 2a performed on site irrespective of the time of day. For participants in Japan, weekly administration of PegIFN- α 2a must be performed at the study site by the investigator or his/her designee.
- e. Participants who discontinue study intervention early will have an early WD visit and will enter follow-up unless they withdraw consent. Participants who withdraw consent will be offered an optional safety follow-up visit to occur on the day of consent withdrawal. For the optional safety follow-up visit, assessments are at the investigator's discretion and could be similar to the early WD visit.
- f. Both the Platform Master ICF and the ISA ICF must be signed before the first study-related activity. For participants who consent to participation in the intensive PK study (optional), the corresponding checkbox in the ISA ICF must be checked.
- g. Minimum criteria for the availability of documentation supporting the eligibility criteria are described in the source documents section in Attachment 3 of the Master Protocol PLATFORMPAHPB2001. Clinical status will be checked and documented at screening and again before first dose of study intervention. If a participant's clinical status changes (including any available laboratory results or receipt of additional medical records) after screening but before the first dose of study intervention is given such that he or she no longer meets all eligibility criteria, then the participant should be excluded from participation in the study.
- h. Medical history also includes mode of HBV transmission, stage of liver fibrosis, and alcohol consumption. Historical HBV DNA, ALT, HBsAg, and HBeAg data, if available, will be recorded in the CRF and/or source documents. Available historical data on previous HBV genotype assessments will also be collected in the CRF. HBeAg status should also be recorded.
- i. Liver disease staging assessments will be performed based on Fibroscan or liver biopsy results, obtained within 6 months prior to screening or at the time of screening (in case of Fibroscan) or within 1 year prior to screening (in case of liver biopsy).
- j. Participants must have absence of signs of cirrhosis or portal hypertension (absence of nodules, smooth liver contour, normal portal vein, spleen size <12 cm) and absence of signs of HCC or clinically relevant renal abnormalities on an abdominal ultrasound performed within 3 months prior to screening or at the time of screening. In case of suspicious findings on conventional ultrasound the participant may still be eligible if HCC or clinically relevant renal abnormalities have been ruled out by a more specific imaging procedure (contrast-enhanced ultrasound, CT or MRI).
- k. HBV genotype will be determined at baseline using a standard genotyping assay if HBV DNA levels are sufficiently high. Available historical data on a previous HBV genotype assessment will also be collected in the CRF. Exploratory genotyping may be performed.
- l. Not applicable for the WD visit.
- m. In between study visits, participants will take NA at home and will bring their NA with them to each study visit. At study visits, NA should be taken on site. Weekly PegIFN- α 2a administration should preferably be done on the same day of the week in the evening by self-injection. A total of 12 injections should be administered, starting at Week 12, with the last injection during Week 23. If desired, participants can also choose to have the weekly administration of PegIFN- α 2a performed on site irrespective of the time of day. For participants in Japan, weekly administration of PegIFN- α 2a must be performed at the study site by the investigator or his/her designee.
- n. Only applicable in case of self-injection.

- o. Participants who are administering PegIFN- α 2a by self-injection will be requested to complete a self-injection tracker. Refer to Section 6.4, Study Intervention Compliance, for more details.
- p. Complete physical examination, including height (only at screening), body weight, skin examination, and other body systems.
- q. For participants with a risk factor (eg, diabetes or hypertension), an ophthalmic examination should be repeated at Week 8 (+/- 3 weeks) at the investigator's discretion in case their condition changes. Any participant experiencing a decrease or loss of vision at any time point during study participation, must have a prompt ophthalmic examination. Medical records of the examination should be collected and assessed by the investigator.
- r. A +/- 3-week visit window is allowed for the ophthalmic examination at Week 24.
